2.2 Analysis sets

The following analysis populations will be used for analysis.

[figure not shown]
- The Enrolled population will include all patients who were enrolled into the study.
- The Full Analysis Set (FAS) comprises all patients to whom the study treatment has been assigned. Following the intention-to-treat principle, patients will be analyzed according to the treatment assigned to at randomization. Mis-randomized patients will be excluded from the FAS.
- The modified Full Analysis Set (mFAS) will include all patients who could have completed Week 12 by the study termination date. That means, all patients which were randomized at least 12 weeks prior to 25-Feb-2019 will be included.
- The Safety population (SAF) will include all patients who took at least one dose of study medication. Patients will be analyzed according to treatment received.

The primary efficacy analysis will be performed on the FAS.

2.3 Patient disposition, demographics and other baseline characteristics

Patient demographic and baseline characteristic data to be collected on all patients include: year of birth, age, sex, race, ethnicity, relevant medical history/current medical condition present before signing informed consent, height, weight, body mass index (BMI), prior concurrent medications, NRS at screening, .

In addition, the following categorizations of continuous variables will be done:

- Age into 18-64 years, 65- 84 years, \geq 85 years;
- Duration of PDN into $<$ 1 year, $>$ 1 - 5 years, $>$ 5 - 10 years, $>$ 10 - 15 years, $>$ 15 - 20 years, and $>$ 20 years;

Duration of PDN is calculated from the start date of PDN as reported on the eCRF until the date of Visit 1.

Demographic and background information will be summarized the FAS population using frequency distributions (for categorical variables) and descriptive statistics of mean, standard deviation, minimum, median and maximum (for continuous variables). Relevant medical history/current medical conditions will be summarized by system organ class and preferred term of the MedDRA dictionary.

2.3.1 Patient disposition

For each study phase (i.e., Screening, Treatment epoch and Treatment withdrawal epoch), the overall number of patients who entered, completed, and discontinued that phase will be summarized including the reasons for discontinuation. The summary of the screening phase will be done for the Enrolled set, for the Treatment and Treatment withdrawal epoch. The analyses will be based on the FAS population.

Patients who prematurely discontinue the study medication will be listed along with the reasons for discontinuation.

2.4 Treatments (study treatment, rescue medication, concomitant therapies, compliance)

2.4.1 Study treatment / compliance

Duration (days) of exposure to double-blind study medication will be summarized by treatment group and treatment phase (Treatment epoch and Treatment withdrawal epoch separately). In addition, the number of subjects with exposure of at least certain time thresholds (any exposure, \geq 1 week, \geq 2 weeks, \geq 4 weeks, \geq 6 weeks, \geq 8 weeks, \geq 10 weeks, \geq 12 weeks) will be displayed.

Compliance will be recorded as source documentation only and not analysed.

The analyses will be based on the SAF population.

2.4.2 Prior, concomitant and post therapies

The number and percentage of patients who used concomitant medications (coded by World Health Organization [WHO] Anatomic Therapeutic Chemical classification [ATC]) will be presented by treatment group and treatment phase (Treatment epoch and Treatment withdrawal epoch separately).

Separate tabulations will be provided for medications taken prior to start of study medication and while a patient is on study drug (i.e. concomitant, between the first day on study drug and the day of last visit). In addition, the PDN medications recorded on the Screening PDN Medication Log will be summarized using a frequency table for each medication. The primary reason for treatment failure will also be tabulated.

Prior medications are defined as drugs taken and stopped prior to first dose of study treatment. For the Treatment epoch concomitant medications are defined as any medication given at least once between the day of first dose of study treatment and the end of the treatment epoch, including those which were started pre-baseline and continued into the treatment period. For the Treatment withdrawal epoch concomitant medications are any medications given at least once between the day of first dose of study medication in the treatment withdrawal epoch, and the end of the epoch, including those which were started pre-baseline or in the treatment period epoch, and continued into the treatment withdrawal epoch.

Non-drug therapies will be listed.

2.4.2.1 Rescue medication

The number and percentage of patients who received rescue medication (Acetaminophen/Paracetamol as reported on the diary page) will also be summarized by treatment and by visit during the double-blind treatment and treatment withdrawal period separately. Visit mapping will be done according to the visit window strategy document (see Section 2.1.1). The dose received will be listed.

Analysis of time to first use of rescue medication will be performed using Kaplan-Meier curves.

Number of patients with at least one intake will also be summarized.

2.5 Analysis of the primary objective

2.5.1 Primary endpoint

The primary efficacy variable will be the change from baseline to Week 12 in the weekly mean of the 24-hour average pain score, using an 11-point Numeric Rating Scale (NRS).

The NRS is captured in the e-diary daily by the patient as the intensity of pain in the past 24 hours. To calculate the weekly mean pain intensity score for a given week, the daily pain

intensity scores collected by the patient in the e-diary during the 7 days of that week will be averaged.

The primary population will be the FAS.

2.5.2 Statistical hypothesis, model, and method of analysis

The aim is to estimate the treatment effect of the investigational drug (EMA401) compared to placebo, for the target population on the primary pain parameter. The definition and the justification of the corresponding primary estimand, as well as the definition of the supplementary and secondary estimands for NRS are detailed in the Estimand Charter. The most recent version of the Estimand charter stored at [REDACTED] available before the database lock will be used as reference.

The primary estimation method is based on an Analysis of Covariance (ANCOVA) model including treatment, sex, use of concomitant pain medication for PDN (yes/no) as factors and age and baseline (mean pain intensity) score as covariate. The analysis will account for different intercurrent events (i.e. events that occur post-randomization) as follows:

- **Changes in doses of concomitant medication for PDN:** Efficacy observations collected during the period of changes in doses of concomitant medication for PDN (compared to baseline) and the 3-days thereafter will be excluded, since they are considered affected by the concomitant medication dose change. The resulting missing data after this step will be imputed via multiple imputation method using the Missing at random (MAR) assumption.
- **Intake of rescue medication:** Efficacy data collected during intake of rescue medication will be used for analysis.
- **Intake of prohibited medications with potential confounding effect prior to study treatment discontinuation:** The prohibited medications with a potential confounding effect are defined as those listed in Table 2-1 requiring study treatment discontinuation. A list of prohibited medications is available at the following [REDACTED] location

[REDACTED]. Efficacy observations collected during the intake period of such prohibited medications and the 7-days thereafter will be excluded, since they are considered affected by the prohibited medication intake. The resulting missing data after this step will be imputed via multiple imputation method using the MAR assumption.

Table 2-1 Prohibited medication

Medication	Prohibition period	Action taken for study treatment
Prohibited prior to Screening and throughout study		
Any skeletal muscle relaxant (e.g. baclofen, orphenadrine, methocarbamol)	2 weeks prior to Screening and after Screening	None
Mexiletine	2 weeks prior to Screening	None

Medication	Prohibition period	Action taken for study treatment
	and after Screening	
Dextromethorphan	2 weeks prior to Screening and after Screening	None
Memantine	2 weeks prior to Screening and after Screening	None
Alpha-lipoic acid	2 weeks prior to Screening and after Screening	None
Other anti-epileptic drugs (e.g. valproic acid, carbamazepine, phenytoin)	2 weeks prior to Screening and after Screening	Discontinue study treatment upon 2 nd episode of medication use
Antiviral medications (e.g. valacyclovir, acyclovir, amantadine, anti-HIV)	2 weeks prior to Screening and after Screening	None
High dose capsaicin patch (8%)	6 months prior to Screening and after Screening	Discontinue study treatment
Prohibited after Screening and throughout study		
Oral or injectable steroids	After Screening	Discontinue study treatment upon 2 nd episode of medication use
Monoamine oxidase inhibitors or any other antidepressants (except stable dosage of SSRI)	After Screening	Discontinue study treatment upon 2 nd episode of medication use
Antipsychotic or neuroleptic medications	After Screening	Discontinue study treatment upon 2 nd episode of medication use
Cannabinoids (e.g. marijuana)	After Screening	Discontinue study treatment upon 2 nd episode of medication use
Prescribed opioids, including codeine	After Screening	Discontinue study treatment upon 2 nd episode of medication use
Prescription systemic pain medication, or topical treatment for PDN, including lidocaine plaster	After Screening	Discontinue study treatment upon 2 nd episode of medication use
Nonsteroidal Anti-inflammatory Drugs (NSAIDs) or any other over-the-counter pain medications	After Screening	None
Any non-drug therapies that could modulate the perception of pain either directly or indirectly (i.e. transcutaneous electrical nerve stimulation (TENS) or surgery)	After Screening	Discontinue study treatment

Medication	Prohibition period	Action taken for study treatment
Other medications that may have potential drug-drug interactions (e.g. felodipine, eplerenone, nisoldipine, ticagrelor, tacrolimus, avasimibe, rifampin, cyclosporine, gemfibrozil, clarithromycin, St. John's Wort; oral, injected or implanted hormonal methods for contraception)	After Screening	None

Retrieved drop-out (RDO) patients are defined as patients who discontinue study treatment and decide to remain in the study by following an abbreviated schedule of assessments.

[figure not shown]
These patients must continue to adhere to protocol requirements (see respective protocol Table 6-2). The design feature of retrieved drop-outs, considered in order to minimize the occurrence of missing data on primary pain parameter, is exploited for the statistical analysis as follows:

- **Permanent discontinuation of study treatment due to AE, lack of efficacy (LoE) and use of prohibited medication:** If retrieved drop-out data are available, these will be used for analysis. If no data was retrieved after study treatment discontinuation, missing data will be multiply imputed based on placebo arm data, i.e. “jump to reference” (J2R) assumption for the EMA401 arm, missing at random assumption for placebo arm (Carpenter, Roger, and Kenward 2013). Of note, alternatively one could build the imputation model based on the RDO data, however, we expect sparse RDO data which will likely hinder us to build an imputation model. More details on the imputation model are specified in Section 5.
- **Permanent discontinuation of study treatment due to other reasons than AE, LoE and use of prohibited medication (including discontinuation due to USM):** If efficacy data collected after study treatment discontinuation are available (retrieved drop-out), then the retrieved drop-out data will be excluded and missing data after study treatment discontinuation will be imputed via multiple imputation method using the MAR assumption.

The multiple imputations will be carried out on the weekly mean pain score. Details on multiple imputation can be found in Section 5 of this document.

The primary objective will be achieved if the EMA401 100 mg b.i.d. dose is statistically significant versus placebo in terms of the primary efficacy variable after multiplicity adjustment. To preserve the family-wise error rate at 2.5% level when comparing the EMA401 100 mg b.i.d. dose versus placebo on the primary and key secondary endpoints (see Section 2.6), statistical testing will be carried out using the following sequentially rejective, weighted Bonferroni-type test using the graphical approach (Bretz et al 2009) mentioned in Figure 2-1.

Figure 2-1 Sequentially rejective, weighted Bonferroni type test using the graphical approach

In the graphical testing procedure given in Figure 2-1, H1 and H2 denote the two null hypotheses of no treatment difference of EMA401 100 mg b.i.d. vs. placebo for the primary efficacy variable NRS and key secondary efficacy variable NPSI total score. The corresponding alternative hypotheses will be EMA401 100 mg b.i.d. is superior to placebo for the NRS and NPSI respectively. In the Figure 2-1 the number in the circle represents the proportion of alpha level to be assigned at the initial stage among the two null hypotheses. The direction and the number in the arrow represent the proportion of the alpha to be propagated to the next hypothesis. Initially, H1 will be tested at the full alpha level (1 sided) 0.025. If H1 is rejected then H2 will be tested also at the full alpha level (1 sided) 0.025.

To facilitate the interpretation of the estimated treatment difference a standardized effect size will be provided and will be calculated based on the results of the ANCOVA analysis.

The same ANCOVA model will be applied at the visits prior to Week 12. Multiplicity adjustment at visits prior to Week 12 will not be carried out.

Summary statistics for absolute values and change from baseline by treatment and visit will be provided for the original measurements (i.e. for the raw data prior to multiple imputation) of the primary efficacy variable. If a measurement is collected under the period of use of prohibited medications or the 7 days thereafter, it will be excluded from the summaries. ■

2.5.3 Handling of missing values/censoring/discontinuations

Handling of missing daily pain score values within a week (within-week imputation)

The 24-hour average pain score is measured daily for seven consecutive days prior to randomization and then every day through the end of the study. At each week, the weekly mean of the seven 24-hour average pain assessments will be calculated.

The weekly mean will be calculated based on the available assessments. If only one measurement is available, the mean will be based on that value. Assessments made under treatment will not be mixed up with RDO data. If there is at least one value among the seven values in one week which is on-treatment, the mean will be calculated based on that.

Handling of missing weekly mean pain score values (weekly mean imputation)

The multiple imputation for the primary variable will be carried out on the weekly mean pain score.

The imputation procedure related to primary analysis is described in Section 2.5.2 while the imputation procedure for the supplementary analyses is included in Section 2.5.4. The details of these imputation rules are specified in the Estimand Charter and in Section 5.

For all analyses, imputation of intermittent missing observations before treatment discontinuation will be carried out following a MAR mechanism for all treatment arms.

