3.2 Rationale for study design

This study will evaluate the safety and efficacy of EMA401 100 mg b.i.d. in the treatment of PDN.

The aim is to estimate the treatment effect of the investigational drug (EMA401 100 mg b.i.d.) compared to placebo, for the target population on the primary pain parameter. The treatment effect of interest accounts for post-randomization events in a way that reflects their possible relationship to the investigational treatment. In particular, the treatment effect of interest:

- shall not be confounded by events which are deemed non informative on the effect of the study medication, even if they may have the potential to confound it (e.g. some changes in concomitant medications), and
- shall account for events reflecting the unfavorable outcome when patients are unable to continue taking the study medication or unable to benefit from it (such as study treatment discontinuations for specific reasons).

Further details are provided in [Section 9.4.2](#).

The standard methodology for the purpose of evaluating safety and efficacy based on the above treatment effect is to conduct a double-blind, placebo-controlled, randomized, parallel group study. Twelve weeks of exposure is required for assessment of treatment response and registration in chronic pain conditions, as indicated in Food and Drug Administration (FDA) and European Medicines Agency (EMA) guidelines. The quarterly unblinded DMC review of safety data, together with clinical assessments every two weeks will ensure patient safety, according to the DMC Charter.

The study will evaluate the potential for a rebound effect of EMA401 in efficacy and withdrawal effect in safety after study drug discontinuation during a treatment withdrawal period designed to minimize bias via a randomized withdrawal design.

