9.4.3 Handling of missing values/censoring/discontinuations

Handling of missing daily pain score values within a week (within-week imputation)

The 24-hour average pain score is measured daily for seven consecutive days prior to randomization and then every day through the end of the study (See Section 6.4.1). At each visit, the weekly mean of the seven 24-hour average pain assessments will be calculated.

The weekly mean will be calculated based on the available assessments. If only one measurement is available, the mean will be based on that value.

Handling of missing weekly mean pain score values (weekly mean imputation)

The multiple imputation for the primary variable will be carried out on the weekly mean pain score.

The imputation procedure related to primary analysis is described in Section 9.4.2 while the imputation procedure for the supplementary analyses is included in Section 9.4.4. The details of these imputation rules will be specified in an Estimand Charter and in the statistical analysis plan prior to unblinding.

For all analyses, imputation of intermittent missing observations before treatment discontinuation will be carried out following a MAR mechanism for both treatment arms.

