5.4 Derivation of index values and scores

For details on handling of missing items and derivation of scores refer to the document "Handling of missing items and derivation of total scores". The most recent version of this document stored at [REDACTED]

[REDACTED] available before the database lock will be used as reference.

5.4.1 11-point Numeric Rating Scale (NRS)

The Numeric Rating Scale (NRS) is an 11–point scale for patient self-reporting of pain. The averaged score will be computed for every week, regardless of visits.

24-hour Average Pain Score

The 24-hour average pain score will be assessed using the 11-point numeric rating scale (NRS) scale ranging from zero to ten.

24-hour Worst Pain Score

The 24-hour worst pain score will also be assessed using the 11-point NRS scale ranging from zero to ten.

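### In a week that contains a stop for adverse event, lack of efficacy or prohibited medication, the SAP's on-treatment-priority rule discards retrieved diary days that the plan says will be used

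*SAP*

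**What the plan says.** The primary variable is a weekly mean of daily diary scores, formed by calendar week: "The averaged score will be computed for every week, regardless of visits" (SAP 5.4.1).

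- **Stops for adverse event, lack of efficacy or prohibited medication.** SAP 2.5.2, repeating protocol 9.4.2: "If retrieved drop-out data are available, these will be used for analysis". The fallback applies only without such data: "If no data was retrieved after study treatment discontinuation, missing data will be multiply imputed based on placebo arm data", which means jump to reference (J2R) for EMA401 and missing at random (MAR) for placebo.
- **Stops for any other reason**, including the Urgent Safety Measures (USM). The same sections exclude retrieved scores and impute under MAR.
- **Within-week rule, protocol 9.4.3.** "The weekly mean will be calculated based on the available assessments". One value is enough, and on-treatment days have no priority.
- **Within-week rule, SAP 2.5.3.** It repeats the protocol rule and then adds "Assessments made under treatment will not be mixed up with RDO data" and "If there is at least one value among the seven values in one week which is on-treatment, the mean will be calculated based on that". Neither sentence distinguishes stop reasons or exempts Week 12.

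SAP section 4, which lists departures from the protocol's analyses, does not mention the added rule.

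**The concern.** In a week with diary entries on both sides of the stop date, the two instructions cannot both be followed for the three named reasons. One says retrieved scores are used. The other sets them aside as soon as a single on-treatment score exists. A programmer has to choose, and the choice sets the primary value for anyone who stops during Week 12.

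The stop date then has a cliff edge. Take a patient who scores 6 on every day after stopping. A stop just before Week 12 gives a Week 12 value of 6.0. A stop one day later, after one on-treatment score of 3, gives 3.0.

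Protocol 3.2 says the treatment effect of interest "shall account for events reflecting the unfavorable outcome when patients are unable to continue taking the study medication or unable to benefit from it". Discarding the days after such a stop fits that aim poorly. The same weekly means also enter the ANCOVA at earlier visits, the responder analyses and the imputation model, which SAP 5.5.1.2 builds on all scheduled time points. The analyses kept in Amendment 1 do not vary the within-week rule.

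**Working it through.** **Scale: the plan's own power figure.** Inputs from protocol 9.8: difference 0.8, SD 2.6, 200 per arm, one-sided alpha 0.025. Power = Φ(0.8 / (2.6 × √(2/200)) − 1.96) = Φ(3.08 − 1.96) = 86.8%, against a stated value of about 85%. Differences of 0.7 and 0.9 give 76.8% and 93.3% (stated 77% and 94%). These figures are not in dispute.

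**One patient.** The scores are assumed, because the documents give no scores after a stop. Let the score be 3 on treatment and 6 after the stop, with k on-treatment days and 7 − k retrieved days in Week 12.

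- SAP 2.5.3 value: 3.0 for any k of at least 1.
- Protocol 9.4.3 value: (3k + 6(7 − k)) / 7. For k = 1 this is (3 + 36)/7 = 5.57.
- Shortfall: 3 × (7 − k)/7.

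| k (on-treatment days) | 1 | 2 | 3 | 4 | 5 | 6 | 7 |
|---|---|---|---|---|---|---|---|
| Shortfall (points) | 2.57 | 2.14 | 1.71 | 1.29 | 0.86 | 0.43 | 0 |

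With the last on-treatment day spread evenly over the week, the average shortfall is 3 × (0 + 1 + … + 6)/(7 × 7) = 3 × 21/49 = 1.29. The single-day case is the extreme.

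**Arm mean.** SAP Amendment 1 reports 137 randomized, so about 68 per arm.

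- Per affected patient: 1.29/68 = 0.019 to 2.57/68 = 0.038 points.
- Standard error of the difference at the planned SD: 2.6 × √(2/68) = 0.45. So 0.038 is under 0.1 standard errors.

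**How many patients.** The documents give neither stop rates nor timing. Assume 10% to 20% stop for these reasons, evenly over 12 weeks.

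- Share stopping in Week 12: 0.10/12 = 0.83% to 0.20/12 = 1.67%.
- Of 68 per arm: 0.57 to 1.13 patients. This is probably high, because SAP Amendment 1 reports many discontinuations due to trial termination, and those patients fall under the other-reason rule.
- Expected shift in one arm: 0.0083 × 1.29 = 0.011 to 0.0167 × 1.29 = 0.021 points.

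A wider range is 5% to 30% stopping and a rise of 1 to 3 points, with the whole rise lost for every affected patient and only in the EMA401 arm. It gives 0.05/12 × 1 = 0.004 to 0.30/12 × 3 = 0.075 points, against the planned 0.8.

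**Responder status.** With an assumed baseline of 6, a value of 3.0 is a 50% improvement and meets both thresholds. A value of 5.57 is (6 − 5.57)/6 = 7% and meets neither.

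**The case against.** The best defence is that the two SAP sections do different jobs. On that reading, 2.5.2 says which data after a stop enter the analysis, and 2.5.3 only says how a mixed week becomes one number. A mixed week would count as an on-treatment week, with 2.5.2 governing from the next week on. SAP 2.5.3 also refers details to the Estimand Charter, which is not available here and may settle the matter. The reading is coherent, but the SAP does not state it, it leaves retrieved Week 12 scores unused, and the protocol's within-week rule has no such priority.

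The defence does limit the point. Patients who stop before Week 12 are untouched at the primary time point: their Week 12 mean is all retrieved, or it is imputed. Keeping the two kinds of score apart is right for other-reason and USM stops.

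Two stronger readings are tempting but unsupported.

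- **That the rule blocks J2R.** A reader might infer that one on-treatment day wrongly keeps a patient with no retrieved scores out of J2R. But protocol 9.4.3 already accepts a single available score as the weekly mean, so without retrieved scores the priority rule changes nothing. Setting Week 12 to missing instead could discard as many as six valid observed scores.
- **That the rule favours EMA401.** It applies in both arms. The net effect depends on which arm has more such stops and on how pain moves afterwards. A patient stopping for lack of efficacy may have high scores on treatment, and protocol 5.6.2 calls for best standard of care after a stop, so later scores could be lower.

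**Conclusion.** The inconsistency is real and concerns the derivation of the primary variable. For the three named stop reasons, SAP 2.5.3 discards retrieved days that SAP 2.5.2 and protocol 9.4.2 would use. It departs from protocol 9.4.3 without being listed in SAP section 4.

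Its effect on the primary result is small. It can be large for one patient (up to 2.57 points, about 1.29 on average, given the assumed 3-point rise), but it is roughly 0.02 to 0.04 points on the arm mean per affected patient in 68. Under the assumed stop rates about one patient per arm or fewer is affected. The sizes rest on assumed scores, rates and timing, and no direction of bias is established. This is a low-severity correction, worth making because it removes a choice between two written rules at almost no cost.

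**What to change.** In SAP 2.5.3, for the primary estimand and its responder counterpart:

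1. Limit the on-treatment-priority sentence to stops for reasons other than adverse event, lack of efficacy and prohibited medication (USM stops stay under it).
2. For those three reasons, state that the mean of the week containing the stop uses all available daily scores, on treatment and retrieved, as in protocol 9.4.3. If none was retrieved that week, the available on-treatment days form the mean, as now. Week 12 is not set to missing while on-treatment scores exist.
3. For the supplementary estimand in which all patients stay on treatment for 12 weeks, keep on-treatment days only.
4. Record the within-week rule in SAP section 4, and align the Estimand Charter if it says otherwise.

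The cost is two sentences in SAP 2.5.3 and one line in section 4. No new data are needed: SAP 2.5.2 already requires the stop reason, and SAP 2.5.3 already requires on-treatment and retrieved scores to be told apart. The change should be made before unblinding. If that has passed, report how many patients have a mixed Week 12 and give the primary result under both derivations.
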